5.2 Exclusion Criteria

Participants are excluded from the study if any of the following criteria apply:

Medical Conditions

1. Participants who did not develop herpes prodromal symptoms within 6 months after randomization in the study;

Version 5.0 Page: 28 of 68

- 2. More than 50% of recurrences that aborted spontaneously (without intervention) in the past 12 months;
- 3. Primary herpes lesion outside the lips (e.g., nose, chin, etc.);
- 4. Abnormal peri-oral skin condition that might affect the normal course of cold sores (e.g., eczema, psoriasis, etc.);
- 5. Oral diseases whose prodromal symptoms may mimic those of herpes labialis, including recurrent oral aphthous disease;
- 6. Oral diseases that might interfere with the evaluation of the efficacy or safety of the treatments, including gingivitis, periodontitis, mucositis, oropharyngeal candidiasis, etc. or upon inspection of the gums and in the judgement of the investigator, are not suitable for study participation;
- 7. Upper full or partial dentures that in the judgement of the investigator, could interfere with study intervention when applied to the upper gum area;
- 8. History of infection known to be resistant to acyclovir family agents;
- 9. Allergy to any acyclovir or its containing agents;
- 10. Milk allergy or known history of hypersensitivity to one of the components of Sitavig;
- 11. Self-reported immunocompromised condition, including self-reported Human Immunodeficiency Virus (HIV) positive and previous bone marrow or organ transplant;
- 12. Self-reported galactose intolerance, lactase enzyme deficiency or glucose galactose malabsorption; this does not include self-reported lactose intolerance;
- 13. Known medical history of renal disease that in the judgment of the investigator is severe;
- 14. Evidence or history of clinically significant (in the judgment of the investigator) hematological, endocrine, pulmonary, gastrointestinal, cardiovascular, hepatic, psychiatric, neurologic diseases, or malignancies within the last 5 years;
- 15. Females who are planning to become pregnant, are pregnant or lactating;
- 16. Participants with a medical disorder, condition, or history of such that could impair the participant's ability to participate or complete this trial in the opinion of the investigator;

Prior/Concomitant Therapy

- 17. Previous vaccination against herpes simplex;
- 18. In the opinion of the investigator, concomitant treatment likely to interfere with acyclovir;
- 19. Use of any drugs (e.g., amikacin, cisplatin) during the study that may interact with acyclovir;
- 20. Use of any topical cold sore treatment that is not study intervention (e.g., dimethecone, menthol, camphor, benzalkonium chloride, beeswax) or cold sore treatment patch/bandage (e.g., Compeed®) or device during the study;

Page: 29 of 68

Version 5.0

- 21. Participants unwilling to avoid the use of any antivirals, oral analgesics, any lip balm or zinc oxide cream, non-steroidal anti-inflammatory drug (including aspirin and probenecid) or topical pain reliever or anesthetic (e.g., benzocaine, lidocaine) as a cold sore treatment during the study;
- 22. Treatment with topical steroids in the oral area within 4 weeks prior to Investigational Medicinal Product (IMP) administration;
- 23. Patients undergoing any cancer treatment (e.g., chemotherapy);
- 24. Immunomodulator medications (immuno-suppressive or immuno-stimulation) within 30 days of randomization;
- 25. Oral or systemic steroids (intravascular, intramuscular or intra-articular, not including inhaled) within 30 days of randomization;
- 26. Prophylactic antiviral treatment during the Screening Phase, Treatment Phase and in the Follow Up phase until the first new investigator confirmed HL outbreak;

Other Exclusions

- 27. Participants unwilling to avoid the use of cosmetics on facial area at the start of prodromal symptoms and throughout the Treatment Phase of the study;
- 28. Facial hair that obscures complete visualization of the cold sore;
- 29. Participants whose occupations make them unlikely to complete a virtual clinic visit within 36 hours of study intervention initiation;
- 30. Participation in another therapeutic trial evaluating new drugs or which could interfere with the evolution of HL lesions or evaluation of the drug in the study within the preceding 30 days;
- 31. Alcoholism or drug abuse within 2 years prior to the Screening Visit or routine consumption of 3 or more alcohol containing beverages per day; Alcohol containing beverages are defined as one beer (5%), one glass of wine (11%) and one shot (40%) hard liquor;
- 32. Positive urine drug screen at Screening; except for participants with a prescription for a drug belonging to a class (such as amphetamines, benzodiazepines, tricyclic antidepressants, SSRIs, and barbiturates) known by approved labeling or a credible medical information source to potentially interfere with and cause a false positive UDS unless the medication is otherwise exclusionary (e.g., opioids). Participants should deny use of illicit drugs.
- 33. Inability to properly understand protocol requirements, to follow the study procedures, to fully use the Science 37 Platform or to start the self-initiation of study intervention;
- 34. Member or first-degree relative of study staff or the Sponsor directly involved in the study;
- 35. Unwilling or unable to comply with all requirements outlined in the protocol;

Prior/Concurrent Clinical Study Experience

36. Previous enrollment in this study.

Version 5.0 Page: 30 of 68

5.3 Lifestyle Considerations

No lifestyle restrictions are required.

5.4 Screen Failures

Screen failures are defined as participants who consent to participate in the clinical study but are not subsequently randomly assigned to study intervention. A minimal set of screen failure information is required to ensure transparent reporting of screen failure participants to meet the Consolidated Standards of Reporting Trials (CONSORT) publishing requirements and to respond to queries from regulatory authorities. Minimal information includes demography, screen failure details, and eligibility criteria.

Individuals who do not meet the criteria for participation in this study (screen failure) cannot be rescreened.

Screen failures will be documented within the Science 37 Platform.

5.5 Run-in Failures

Run-in failures are participants who successfully completed screening and randomized to a blinded study intervention (treatment). Participants start a 6-month eligibility window during the Run-in Phase where they could potentially self-initiate treatment.

All Run-in failures and the reason for the failure will be documented in the Science 37 Platform and stored in the clinical database.

5.6 Criteria for Temporarily Delaying Study Intervention Administration

Not applicable

6. Study Intervention(s) and Concomitant Therapy

The study center/pharmacy will dispense a blinded treatment after successfully completing screening and baseline assessments. The blisters of investigational medicinal product (IMP) for each treatment will be dispensed using a computer generated randomization schedule.

6.1 Study Intervention Administered

During screening participants who meet the entry criteria will be sequentially assigned to a unique number in ascending order (randomization number, RNR) according to the

Page: 31 of 68

Version 5.0

randomization schedule prepared prior to the study. A separate kit number (and corresponding kit) will be assigned by the interactive (x-voice/web) response system (IXRS) that correlates to the blinded study intervention assigned when the subject was randomized.

Participants will be numbered according to the following scheme:

14001XXXXX

14 = country code (USA)

001 = site number (for site 1)

XXXXX = RNR (starting with 10001)

Whereas the "Xs" will be replaced with a five digit sequentially assigned number as each subject enters the study (e.g., first subject number at Site 1 of the study will be 1400110001).

Once a number has been assigned to a participant, it cannot be reassigned to another participant.

Participants who do not meet all of the eligibility criteria will not be randomized. Upon successful completion of all screening assessments, randomization and participant's receipt of study intervention, participants then enter the Run-In Phase in which they are eligible to start study intervention. At the first sign of prodromal symptoms, participants may self-initiate study intervention which automatically moves them into the Treatment Phase and one of two blinded study interventions:

- Sitavig® (acyclovir) 50 mg muco-adhesive buccal tablet (one tablet application on Day 1);
- Placebo muco-adhesive buccal tablet (one tablet application on Day 1).

Participants will apply one (1) muco-adhesive buccal tablet to the upper gum of the mouth on the same side of the mouth where the prodromal symptoms started. Any dosing-related deviations outside of the allowable window (e.g., >1 hour after the start of prodromal symptoms, second tablet administered) will be documented in the Science 37 Platform (see Section 6.5).

Study intervention is defined as any investigational intervention(s), marketed product(s) or placebo intended to be administered to a study participant according to the study protocol.

Version 5.0 Page: 32 of 68

6.2 Identity of Study Interventions

Table 1 - Study Interventions

| Intervention | Test | Reference | | | |
|-------------------------|-----------------------------|-----------------------------|--|--|--|
| UI Number | 1614773 | 1614773-003 | | | |
| Туре | Drug | Placebo | | | |
| Dose Formulation | acyclovir | | | | |
| | hypromellose | hypromellose | | | |
| | milk protein concentrate | milk protein concentrate | | | |
| | sodium lauryl sulfate | sodium lauryl sulfate | | | |
| | magnesium stearate | magnesium stearate | | | |
| | microcrystalline cellulose | microcrystalline cellulose | | | |
| | povidone | povidone | | | |
| | colloidal silicon dioxide | colloidal silicon dioxide | | | |
| Dose Strength | 1 tablet | 1 tablet | | | |
| Dosage | 50 mg | Not applicable | | | |
| Route of Administration | Oral (upper gum area) | Oral (upper gum area) | | | |
| Packaging and Labeling | Study Intervention will be | Study Intervention will be | | | |
| | provided in a blister. Each | provided in a blister. Each | | | |
| | blister will be labeled as | blister will be labeled as | | | |
| | required per FDA | required per FDA | | | |
| | requirements | requirements | | | |
| Batch Number | available in the study file | available in the study file | | | |
| Manufacturer | Farméa | Farméa | | | |
| | [name] | [name] | | | |
| | [name] | [name] | | | |
| | [name] | [name] | | | |

All study drugs will be manufactured and labeled according to Good Manufacturing Practice (GMP) and applicable local laws. Label text will be approved according to the sponsor's agreed procedures, and a copy of the labels will be made available to the study site upon request.

For all study drugs, a system of numbering in accordance with all requirements of GMP will be used, ensuring that each dose of study drug can be traced back to the respective bulk batch of the ingredients. Lists linking all numbering levels will be maintained by the sponsor's clinical supplies Quality Assurance (QA) group.

A complete record of batch numbers and expiry dates of all investigational products as well as the labels will be maintained in the clinical supply file.

The source of test and reference products will be documented in the clinical supply file.

6.3 Preparation/Handling/Storage/Accountability

Only participants randomized in the study may receive study intervention and only authorized staff may supply study intervention. All study intervention must be stored in a secure, environmentally controlled, and monitored (manual or automated) area in accordance with the labeled storage conditions with access limited to authorized staff.

The investigator's delegated staff is responsible for study intervention accountability, reconciliation, and record maintenance (i.e., receipt, reconciliation, and final disposition records).

Further guidance and information for the final disposition of unused study interventions are provided in a separate document.

Version 5.0

Page: 33 of 68

6.4 Measures to Minimize Bias: Randomization and Blinding

| Study using Pre- Coded Randomization provided to the site | At Screening, qualified participants will be assigned a unique number (randomization number, [RNR]) in ascending numerical order. The randomization number encodes the participant's treatment assignment to one of the two arms of the study, according to the randomization schedule generated prior to the study by the Statistics Department at Bayer. Each participant will be dispensed blinded study intervention, labeled with his/her unique randomization number, throughout the study. The treatment kit number will be pre-printed on the study intervention (treatment) kit package. |
|---|--|
| Blind Break | The IXRS will allow the investigator to see (unblind) the study intervention assignment for each participant should it be medically necessary (as it relates to a SAE). Participants who are unblinded during the Treatment Phase of the study will not be included in the Treatment Phase analysis. Participants who are unblinded during the Follow-up Phase will not be included in the Follow-up analysis. In case of an emergency, the investigator has the sole responsibility for determining if unblinding of a participant's intervention assignment is warranted. Participant safety must always be the first consideration in making such a determination. If the investigator decides that unblinding is warranted, the investigator should make every effort to contact the sponsor prior to unblinding a participant's intervention assignment unless this could delay emergency treatment of the participant. If a participant's intervention assignment is unblinded, the sponsor must be notified within 24 hours after breaking the blind. In the event of a Quality Assurance audit, the auditor(s) will be allowed access to unblinded study intervention records to verify that randomization/dispensing has been done accurately. If necessary, Bayer Pharmacovigilance may unblind the intervention assignment for any participant with an SAE. If the SAE requires that an expedited regulatory report be sent to one or more regulatory agencies, a copy of the report, identifying the participant's intervention assignment, may be sent to investigators in accordance with local regulations and/or sponsor policy. |

Version 5.0 Page: 34 of 68

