9.2 Sample Size Determination

9.3 Analysis Set

For the purposes of analysis, the following analysis sets are defined:

Table 2 - Analysis Populations

| Participant Analysis Set | Description |
|--------------------------|--|
| Safety | All randomized subjects who take at least one dose of IMP. Safety analyses will be conducted on the safety population. |
| Intent To Treat (ITT) | All subjects who are randomized and provide at least one measure of primary efficacy parameters after the 1 st dose of IMP. |
| Per Protocol (PP) | The Per Protocol population will include all subjects in ITT who complete 14-days of evaluations and do not have any major protocol violations. Any exclusion from PP Population will be determined and documented prior to the database lock. |
| | The primary efficacy analysis population will be PP population and ITT Population will be secondary. The same analysis on ITT Population will be repeated for the primary and secondary efficacy endpoints to assess the robustness of the results based on PP Population. |

Version 5.0 Page: 49 of 68

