9.5 Treatment Phase Analysis

The statistical analysis will be performed upon completion of all study participants who complete the Treatment Phase (up to Day 14). The additional analysis of treatment follow-up will be conducted upon completion of follow-up phase (up to 12 months). The SAP will provide further details about those planned analyses.

ersion 5.0 Page: 51 of 68

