6 ANALYSIS POPULATION AND TREATMENT GROUPS

6.1 Analysis Population

Screened Population: All subjects who signed the Informed Consent Form.

Safety Population: All randomized subjects who take at least one dose of IMP.

Intent-to-treat (ITT) Population: All subjects who are randomized and provide at least one measure of primary efficacy parameters after the first dose of IMP i.e., if there is at least one non-missing assessment of subject's face image using a 6-point Likert scale after study drug initiation.

PP Population: The Per Protocol population will include all subjects in ITT who complete 14-days of evaluations and do not have any major protocol violations. Any exclusion from PP Population will be determined and documented prior to the database lock.

Follow-Up Population: The Follow Up population will be a subgroup of the ITT population who will continue into the 12 month follow up period and will be defined as patients whose lesions were all treated at the end of the Treatment Phase (of 14 Days) of the trial.

CONFIDENTIAL Page 20 of 31

Private and Confidential Study No 21755 Date: DEC 18, 2023

The primary efficacy analysis population will be PP population and ITT Population will be secondary. The same analysis on ITT Population will be repeated for the primary and secondary efficacy endpoints to assess the robustness of the results based on PP Population.

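### Protocol 6.4 excludes unblinded participants from analysis, with unblinding tied to SAEs; this contradicts the analysis sets in protocol 9.3 and SAP 6.1, and neither document says which rule prevails

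*Protocol*

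**What the plan says.** The Blind Break entry in protocol 6.4 allows the investigator to unblind through the IXRS "should it be medically necessary (as it relates to a SAE"). It then sets two exclusion rules. For the Treatment Phase: "Participants who are unblinded during the Treatment Phase of the study will not be included in the Treatment Phase analysis". For Follow-up: "Participants who are unblinded during the Follow-up Phase will not be included in the Follow-up analysis". Neither sentence is limited to efficacy. Later in the same entry come emergency unblinding at the investigator's judgement, auditor access to unblinded records, and a sponsor route: "If necessary, Bayer Pharmacovigilance may unblind the intervention assignment for any participant with an SAE".

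Protocol 9.5 does not narrow the term used in 6.4. Under the title Treatment Phase Analysis it says: "The statistical analysis will be performed upon completion of all study participants who complete the Treatment Phase (up to Day 14"), with a further analysis after follow-up.

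The analysis sets read differently. Protocol Table 2 (section 9.3) defines Safety as "All randomized subjects who take at least one dose of IMP. Safety analyses will be conducted on the safety population". SAP 6.1 has the same definition: "Safety Population: All randomized subjects who take at least one dose of IMP". ITT needs randomization and at least one post-dose primary efficacy measure. PP adds 14 days of evaluations and no major violation. Follow-Up is a subgroup of ITT. None of the four definitions mentions unblinding, and nor does SAP 2.5 on blinding. SAP 7.13 lists one change from the protocol, which concerns the recurrence-incidence test.

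**The concern.** An exclusion triggered by unblinding would be a minor matter if unblinding were unrelated to outcome. Here the main route to it is a serious event, usually after dosing. Three things are at stake.

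- **Safety.** Assessing safety and tolerability is a stated secondary objective, measured by TEAE incidence, and SAP 7.8.1 plans dedicated tables of serious TEAEs. A rule that can drop participants because they had an SAE acts on the cases those tables exist to show.
- **ITT.** ITT is the plan's robustness check on a primary analysis in PP. It should not lose participants because of an event after randomization.
- **Recurrence.** The Follow-up sentence would take a participant out of the recurrence analyses altogether, although SAP 7.7.2 already censors subjects without recurrence at last follow-up.

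A programmer who applies 6.4 complies with the protocol, and one who applies SAP 6.1 complies with the SAP. The two can produce different tables.

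**Working it through.** The plan gives no figure to reproduce. The check is a comparison of text, followed by bounds on the effect.

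**Step 1. What each rule does with a dosed participant who has an SAE and is unblinded in the Treatment Phase.**

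| Analysis | Under protocol 6.4 as worded | Under protocol 9.3 and 9.4.5, SAP 6.1 and 7.8 |
|---|---|---|
| Safety tables | Out (no safety exception) | In (dosed) |
| ITT efficacy | Out | In, if one post-dose image is scored |
| PP efficacy | Out | In, unless 14 days are incomplete or a major violation is recorded; unblinding is not named as one |

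For unblinding during follow-up, 6.4 removes the participant from the Follow-up analysis, while SAP 6.1 and 7.7.2 keep the participant in the Follow-Up population for recurrence.

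**Step 2. Does any text give one rule priority?** Protocol 9.4.1 delegates the description of populations to the SAP, which favours SAP 6.1. But the SAP never mentions the 6.4 rule, and SAP 7.13 does not declare a departure from it. No sentence ranks the two.

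**Step 3. Who counts as unblinded?** The exclusion sentences directly follow the one on investigator unblinding. Pharmacovigilance and audit access come later in the entry, with no exclusion attached. Whether sponsor-only access triggers exclusion is therefore unclear.

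**Step 4. Bounds.** Let n be the number dosed in an arm, x the number with a serious TEAE, and u the number of those who are unblinded in the phase analysed. Ignore unblinding for any other reason. The table then shows:

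- analysis sets govern: x/n
- 6.4 governs: (x − u)/(n − u)

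With u = 0 the two agree. With u = x the table shows zero, whatever the true rate.

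The documents available supply none of n, x or u. The table below is therefore purely an illustration, with assumed x = 3 and assumed n of 100, 150 and 300. Each cell gives the observed proportion and, in parentheses, the exact (Clopper–Pearson) two-sided 95% upper limit. For a zero count that limit is 1 − 0.025^(1/(n − u)).

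| n (assumed) | u = 0 | u = 1 | u = 2 | u = 3 |
|---|---|---|---|---|
| 100 | 3/100 = 3.0% (8.5%) | 2/99 = 2.0% (7.1%) | 1/98 = 1.0% (5.6%) | 0/97 = 0% (3.7%) |
| 150 | 3/150 = 2.0% (5.7%) | 2/149 = 1.3% (4.8%) | 1/148 = 0.7% (3.7%) | 0/147 = 0% (2.5%) |
| 300 | 3/300 = 1.0% (2.9%) | 2/299 = 0.7% (2.4%) | 1/298 = 0.3% (1.9%) | 0/297 = 0% (1.2%) |

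This shows only the direction and form of the effect if 6.4 were applied. It does not estimate what will happen in this trial.

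**The case against.** The strongest reply is that the specific rules already protect safety. Table 2, protocol 9.4.5, SAP 6.1 and SAP 7.8 all place the safety analyses on every dosed subject, the protocol leaves populations to the SAP, and the SAP was written from protocol version 5.0 without an unblinding exclusion. Individual listings are planned, and SAEs are reported through a separate route. Followed as written, the SAP loses no dosed subject from safety.

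That stands, and it rules out a stronger reading: a reader might infer that SAE cases will be removed from the safety evaluation. The documents do not support this. Removal happens only if 6.4 is applied over the analysis-set definitions.

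Two further inferences also go too far. One is that every SAE leads to exclusion: unblinding in 6.4 is conditional on medical necessity or on pharmacovigilance judging it necessary. The other is that pharmacovigilance-only access certainly triggers exclusion: the text leaves this open.

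It can also be said that ITT is only the secondary efficacy population and already requires dosing and a post-dose image, so it is not the full randomized set. That is true, and no figure shows a material effect on efficacy. But these limits do not justify a further exclusion that depends on a serious event.

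What survives is the contradiction. The 6.4 wording is explicit, is not limited to efficacy and is not reconciled anywhere.

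**Conclusion.** The documents contain two incompatible rules on whether unblinded participants are analysed. The rule in 6.4 depends on outcome, because it ties investigator unblinding to SAEs. The effect lies between two bounds: nobody is lost from the Safety population if Table 2 and SAP 6.1 govern; every unblinded SAE case is lost from the safety tables, and from ITT and the recurrence analyses where it would otherwise count, if 6.4 governs. The position between these bounds is unknown, because arm size, SAE rate and unblinding rate are not given.

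Confidence is high that the conflict exists. No bias in the safety results is demonstrated. The point should be settled before database lock, because the choice affects a stated safety objective and the population used to check the primary result.

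**What to change.** In SAP 6.1, state that:

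- unblinding does not remove a subject from the Safety, ITT or Follow-Up populations;
- unblinding of the participant, the investigator or the image reader is reviewed as a possible major deviation for PP only, with the decision documented before database lock;
- access to the assignment by sponsor pharmacovigilance or auditors alone is not a reason for exclusion.

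Record the departure from protocol 6.4 in SAP 7.13. Add a listing of unblinded subjects showing who was unblinded, when and why. Correct the two exclusion sentences in protocol 6.4 at the next amendment.

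**Cost.** The SAP change is wording and one listing, with no new data. The protocol correction needs IRB/IEC approval under protocol 10.1.1, which is why it can wait for the next amendment once the SAP is clear. The downside is that a few assessments made after unblinding stay in ITT and Follow-Up. The listing lets a reader judge how many.
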